4.2 Patients Registration and Enrollment

Patients must have signed and dated all applicable consents and authorization forms to be registered in the Velos eResearch database system, which is sponsored by The University of Oklahoma Stephenson Cancer Center (OU-SCC).

A Screening identification (Screening ID) number will be provided by OU-SCC research staff. After all screening procedures and assessments have been completed and eligibility has been established, the subject Study ID number will be generated by OU-SCC. Once the patient has been provided a Study ID number, only the Study ID number should be used. Both patient ID numbers should be documented in Velos.

Patients must not start protocol treatment prior to registration and enrollment. A patient will start protocol treatment only after the pre-treatment evaluation is complete and eligibility criteria have been met.

[figure not shown]
NOTE: Per the Institutional Review Board (IRB) reporting, a patient is considered accrued once he or she signs a consent form for the study. A patient is considered enrolled once the patient begins treatment. Evaluable patients are defined in protocol Section 8.2.1.

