10.2 Analytic Plan

Only evaluable patients as defined in Section 8.1.1 will be included in the statistical analysis. The proportion of patients receiving a complete induction course (at least 5 of 6 treatments of each BCG and avelumab within eight weeks of starting treatment) at 3 months and at 6 months will be calculated and a 95% Wilson score confidence interval constructed for the completion rate.

The 3-month and/or 6-month complete response (CR) rates will be summarized as the proportion (and 95% CI) of patients with complete tumor response at month 3 or 6 of study treatment.

Kaplan-Meier curves will be generated for overall survival, duration of response, progression-free survival, cystectomy-free survival, time to recurrence, and time to high-grade recurrence. Median survival time and 95% confidence intervals will be calculated. The EORTC QLQ-C30 questionnaire functional scales, symptom scales, and global health and quality of life scale will be summarized.

Frequency and severity of adverse events will be tabulated by body system, type and maximum grade. Serious adverse events will be listed.

Interim analysis

An interim safety analysis will be conducted when 3~6 patients have received ≥ 5 doses of BCG treatment in dose level 1. If the combination therapy in dose level 1 is not tolerated (2 or more patients experience a DLT), dose level -1 will be evaluated in additional 3~6 eligible patients. The decision rule is fully described in Section 5.2 Overall Study Design.

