- xxvii. Administration of a live/attenuated vaccine within 4 weeks prior to the first dose of study treatment, within 5 months following the administration of the last dose of study drug, or anticipation that such a live/attenuated vaccine will be required during the study.
- xxviii. Other severe acute or chronic medical conditions including immune colitis, inflammatory bowel disease, immune pneumonitis, pulmonary fibrosis or psychiatric conditions including recent (within the past year) or active suicidal ideation or behavior; or laboratory abnormalities that may increase the risk associated with study participation or study treatment administration or may interfere with the interpretation of study results and, in the judgment of the investigator, would make the patient inappropriate for entry into this study.

5. Analysis Populations

The analysis populations are defined as below.

- a. **Safety population:** All patients who receive at least one dose of combination avelumab and BCG will be included in the analyses of compliance and safety.
- b. **Biomarker population:** For biomarker analysis, the biomarker population will comprise all evaluable patients who have sufficient baseline and on-study biomarker measurements.
- c. **Evaluable population:** Evaluable patients will be defined as patients who receive at least 5 doses of intravesical BCG and avelumab IV weekly during induction treatment and complete the first post-treatment cystoscopy and/or urine cytology for tumor assessment. Patients

who discontinued study treatment due to toxicity incurred by previous therapy will be evaluated for safety analysis, but will be replaced by additional patients for the efficacy analysis.

Patients removed from study for early withdrawal or hypersensitivity reactions will be replaced if they have received less than 5 doses of study treatment during induction treatment, but will be included in the safety analysis.

Patients who do not receive at least 5 doses of intravesical BCG and avelumab IV during induction treatment will be considered unevaluable for efficacy analysis and will be replaced unless the missed doses were due to development of grade 3-4 adverse events related to study treatment.

Evaluable population will be used for the analysis of EORTC QOQ-C30 (Section 6) and antitumor measures (Section 8).

6. Patient Population Summary

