5. The following may be considered as exceptions to DLTs: 1.
- a. Grade 3 nausea, vomiting, or diarrhea and Grade 4 vomiting or diarrhea in the absence of maximal medical therapy that resolves in 72 hours.
 - b. Grade 3 fatigue lasting < 5 days.
 - c. Grade 3 hypertension that can be controlled with medical therapy.
 - d. An increase of indirect (unconjugated) bilirubin indicative of Gilbert's syndrome.
 - e. Serum lipase and/or serum amylase CTCAE Grade 3 ≤ 7 consecutive days without clinical signs or symptoms of pancreatitis.

ii. **Definition of DLT Evaluable Population**

1. Patients enrolled in safety lead-in cohort who receive at least 4 doses and complete the DLT observation period (the first 42 days of induction treatment), unless the patient discontinued the study treatment due to a DLT.

8. Antitumor Evaluation

- a. The proportion of patients receiving a complete induction course (at least 5 of 6 treatments of BCG + avelumab within eight weeks of starting treatment) at 3 months and at 6 months will be calculated and a 95% Wilson score confidence interval constructed for the completion rate.
- b. The 3-month and/or 6-month complete response (CR) rates will be summarized as the proportion (and 95% CI) of patients with complete tumor response at month 3 or 6 of study treatment. Patients who remain CR at end of study (EOS) are censored at their last cystoscopy date.
- c. The duration of response will be calculated as time from the date of first response (complete response (CR), partial response (PR), pathological complete response (pCR)) to the first date of non-response. Duration of response will be summarized using the Kaplan-Meier method. Median duration of response with 95% CI will be computed. Results will be presented in tabular and graphic form, as appropriate.
- d. Progression-Free Survival (PFS) at six month and twelve months is defined as the time in months from the first dose of the drug to the date of death or the first documented date of progression, whichever comes first. For patients who did not die and did not have progression, the PFS is censored at the last documented tumor assessment. Survival curve for PFS will be generated using the Kaplan-Meier method. Median PFS with 95% CI will be computed. Those without an event are censored at their last valid tumor assessment, or at the last tumor assessment before patient start of the new therapy if a patient has started new anti-cancer therapy.

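### Read literally, SAP 5.c puts the primary induction-completion rate (SAP 8.a) in a set that already requires at least 5 induction doses, contrary to the at-least-one-dose set in the Protocol and SAP 5.a

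*SAP*

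**What the plan says.** **SAP 5.c, Evaluable population.** The definition opens: "Evaluable patients will be defined as patients who receive at least 5 doses of intravesical BCG and avelumab IV weekly during induction treatment". It also requires that patients "complete the first post-treatment cystoscopy and/or urine cytology for tumor assessment". Patients below 5 doses "will be considered unevaluable for efficacy analysis and will be replaced unless the missed doses were due to development of grade 3-4 adverse events"; this exception is limited to events attributed to the study drugs. A separate paragraph replaces patients removed for early withdrawal or hypersensitivity with fewer than 5 doses, and keeps them for safety only. The section closes with the assignment: "Evaluable population will be used for the analysis of EORTC QOQ-C30 (Section 6) and antitumor measures (Section 8".

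**SAP 8.a, first item of the Antitumor Evaluation section.** "The proportion of patients receiving a complete induction course (at least 5 of 6 treatments of BCG + avelumab within eight weeks" is to be calculated with a 95% Wilson interval. SAP 7.a restates the primary endpoint under DLT Analysis but gives only dose-decision rules, with no proportion or interval.

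**SAP 5.a, Safety population.** "All patients who receive at least one dose of combination avelumab and BCG will be included in the analyses of compliance and safety".

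**Protocol.** Section 8.1, headed Safety Evaluation, defines the induction-completion rate. Its subsection 8.1.1 defines the evaluable set for safety as patients with at least one dose of BCG and avelumab. Section 10.2 says "Only evaluable patients as defined in Section 8.1.1 will be included in the statistical analysis" and goes straight on to the completion proportion. Sections 1.2 and 6.4 class as treatment failures the patients who cannot tolerate 5 of 6 treatments, or who do not receive 5 BCG doses within eight weeks.

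**The concern.** The primary question is whether patients can get through induction. A denominator that admits only patients with at least 5 doses removes most of those who could not, and these are the patients the Protocol calls failures. An analyst following the SAP's numbered cross-reference and one following Protocol 10.2 could report different primary rates from the same data.

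The grade 3-4 exception in SAP 5.c repairs this only in part. It is unclear whether it overrides the 5-dose condition in the opening sentence or merely spares these patients from being called unevaluable and replaced. It does not cover lower-grade toxicity. A DLT by dose delay of more than 2 weeks (SAP 7) has no grade threshold, so a patient stopped short of 5 doses by such a delay can fall outside the exception. The hypersensitivity paragraph carries no grade exception, although a grade 3 hypersensitivity reaction is a DLT, and the SAP does not say which paragraph governs.

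**Working it through.** **1. The plan's own figure.** The documents give no expected rate or precision for induction completion. The one reproducible figure is the Wilson lower bound for Month 6 completion (Protocol 10.1, SAP 3.b): n = 18, rate 60%, lower bound 37.6%.

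Wilson interval: [p + z²/(2n) ± z√(p(1−p)/n + z²/(4n²))] / (1 + z²/n), with z = 1.96 and z² = 3.84.

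With p = 0.60 and n = 18: centre (0.600 + 0.1067)/1.2134 = 0.5824; half-width 1.96 × √(0.01333 + 0.00296)/1.2134 = 0.2062. The interval is 37.6% to 78.9%. The stated bound reproduces, and this point does not affect it.

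**2. Two denominators, same data.** Assumed counts, not from the documents: 20 treated, 18 complete induction.

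| Set | Rate | Wilson 95% CI |
|---|---|---|
| At least one dose (SAP 5.a, Protocol 8.1.1) | 18/20 = 90.0% | 69.9-97.2 |
| SAP 5.c, both non-completers dropped, all completers assessed | 18/18 = 100% | 82.4-100 |
| SAP 5.c, both non-completers kept, one completer unassessed | 17/19 = 89.5% | 68.6-97.1 |

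The third row shows that the direction is not fixed, because the assessment requirement can also remove completers.

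**3. General form.** Let p be the true completion rate, a the share of completers who are assessed, and f the share of non-completers kept in the 5.c set. The expected reported rate is

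r = pa / [pa + (1 − p)f],

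which exceeds p only when a > f. The documents give none of the three values. The 60% in Protocol 10.1 concerns Month 6 maintenance, so p is varied here. With a = 1, for example p = 0.80 and f = 0.25: r = 0.80/(0.80 + 0.20 × 0.25) = 0.80/0.85 = 94.1%.

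Each cell gives the expected reported rate, then the coverage of the true p by the planned Wilson interval. Coverage is the sum of Binomial(18, r) probabilities over outcomes whose interval contains p.

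| True p | f = 0 | f = 0.25 | f = 0.5 | f = 0.75 | f = 1 |
|---|---|---|---|---|---|
| 60% | 100%; 0% | 85.7%; 25.0% | 75.0%; 69.4% | 66.7%; 89.4% | 60.0%; 94.7% |
| 80% | 100%; 0% | 94.1%; 66.4% | 88.9%; 87.8% | 84.2%; 93.9% | 80.0%; 93.1% |
| 90% | 100%; 100% | 97.3%; 100% | 94.7%; 99.8% | 92.3%; 99.0% | 90.0%; 97.2% |

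At f = 0 every result is 18/18, with lower bound 18/(18 + 3.84) = 82.4%, so the interval misses every true rate below 82.4%. At p = 90% the interval still covers the truth, although the point estimate is too high. With a = 0.95 and p = 90%, the reported rates at f = 0, 0.25, 0.5 and 1 are 100%, 97.2%, 94.5% and 89.5%.

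**The case against.** The strongest reply is that the Protocol already settles the set. It defines completion under Safety Evaluation, directly above the at-least-one-dose definition, and Section 10.2 cites that definition just before describing the proportion. SAP 5.a gives compliance analyses to the same set. Dose completion is not an antitumor measure, so 8.a is probably just in the wrong section. This stands, and it fixes the direction of the correction. It does not remove the need for one: SAP 5.c cites Section 8 by number without exempting 8.a, and SAP 5.a does not name the completion rate.

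Four stronger readings are tempting and are not supported.

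- **The Protocol contradicts itself on this analysis set.** Section 4.2 does say "Evaluable patients are defined in protocol Section 8.2.1", which is the 5-dose set. That is a note on accrual and enrolment status for IRB reporting, not an analysis instruction, and 8.1.1 and 8.2.1 are titled separately for safety and efficacy.
- **The primary rate is 100% by construction.** That needs f = 0 and no other route to failure. The natural reading of the exception keeps assessed patients with related grade 3-4 events, and most DLT criteria are grade 3 or higher, so the toxicity-defined endpoint of SAP 2.a is less exposed than all-cause completion. SAP 5.c, unlike Protocol 8.2.1, has no eight-week window, so a patient with a late fifth dose could be evaluable yet not a completer. Because one drug may continue while the other is held (Protocol 6.4), a patient could have 5 doses of each drug but fewer than 5 joint treatments. Whether that is failure depends on how the endpoint is read; Protocol 8.1 counts each drug.
- **The reported rate is always too high.** The 17/19 case shows otherwise.
- **Dose decisions are compromised.** They rest on DLTs in the DLT-evaluable set. The delay-only DLT argument is also narrower than it looks, since SAP 7 ties DLT monitoring to the safety lead-in.

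**Conclusion.** The point holds as a conflict between the SAP's numbered cross-reference and the set indicated by the Protocol and SAP 5.a. Followed literally, SAP 5.c conditions the denominator of the primary rate nearly on success. Confidence is high for this textual mismatch, and lower for any particular bias, because the documents do not say how many non-completers would be kept or how many completers would be assessed. In the 20-patient illustration the effect ranges from 10 percentage points upward (90.0% to 100%) to half a point downward (89.5%). It is small when most non-completers are kept.

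What is at stake is the reported primary result. There is no hypothesis test, and the sample size was set by feasibility. This should be fixed before the primary analysis.

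**What to change.** - **SAP 5.c and 8.a:** state that induction completion is analysed in the Safety population (SAP 5.a, Protocol 8.1.1), either by exempting 8.a from 5.c or by moving it out of Section 8. Cross-refer SAP 7.a to the same analysis.
- **Replacement:** state that replaced patients stay in this denominator as non-completers and that their replacements add to it.
- **Dose level:** if de-escalation occurs, report the rate by dose level, so that patients treated at dose level 1 are not dropped.
- **Reporting:** give the all-cause completion proportion, with reasons for non-completion, next to the toxicity-defined endpoint of Protocol 2.2.1 and SAP 2.a.
- **Antitumor endpoints:** the Evaluable population may stay for 8.b onward, provided Protocol 10.2 is reworded to match, since it now applies the at-least-one-dose set to the whole statistical analysis.

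The cost is a few sentences in the SAP and one Protocol clarification, with no new data or patients. The downside is that the reported rate may be less favourable and its denominator may exceed 18.

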a repeat induction of BCG for patients with disease refractory to the first BCG induction only has a response rate of around 20%. Cystectomy is offered to patients who have high risk NMIBC and those who may be resistant to BCG. However, few patients want to undergo such a radical surgery. Improvements in BCG treatment, particularly the addition of systemic immunotherapy may lead to improved response rates, decreased rates of recurrence and better survival without the need for cystectomy.

Patients undergoing BCG therapy must be able to tolerate induction therapy. For any strategy to improve the anti-cancer efficacy of intravesical BCG completion of induction therapy is required. This study includes a safety lead-in to ensure patients tolerate the combination therapy of full dose BCG and a novel weekly dosing of avelumab. BCG has been shown to be effective in split dosing. If patients are not tolerant of full dose BCG, reduced dosing will be evaluated. For this study to proceed, patients must be able to tolerate induction therapy as commonly defined as receiving at least 5 of 6 weekly treatments within an 8 week period. The completion of a full induction course within eight weeks of starting treatment is the primary endpoint of this study. Patients who cannot tolerate 5 of 6 weekly treatments as part of induction therapy will be considered treatment failures.

The response to treatment at the 6 month mark has been shown to be predictive of further tumor recurrence [11]. A secondary endpoint of this study will be the rate of completion of the 6 month maintenance course which will simultaneously evaluate for tolerance of therapy at 6 months and disease response. This measure will provide a clinically meaningful endpoint of both safety and efficacy.

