8.2.1 Definition of Evaluable Patients for Efficacy Analysis

Evaluable patients will be defined as patients who receive at least 5 doses each of intravesical BCG and avelumab IV during induction treatment (first 8 weeks) and complete the first post-treatment cystoscopy and/or urine cytology for tumor assessment. Patients who discontinued study treatment due to toxicity incurred by previous therapy will be evaluated for safety analysis, but will be replaced by additional patients for the efficacy analysis.

Patients removed from study for early withdraw or hypersensitivity reactions will be replaced if they have received less than 5 doses of study treatment during induction treatment, but will be included in the safety analysis.

Patients who do not receive at least 5 doses of intravesical BCG and avelumab IV during induction treatment will be considered unevaluable for efficacy analysis and will be replaced unless the missed doses were due to development of grade 3-4 adverse events related to study treatment.

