- e. Overall survival (OS) is defined as time in months from first dose of the drug to the date of death. Patients who are still alive at EOS are censored on the date they were last known to be alive. Survival curve for OS will be generated using the Kaplan-Meier method. Median OS with 95% CI will be computed. If overall survival cannot be calculated due to no patient deaths, it will not be reported.
- f. Recurrence free survival (RFS) at 6 and 12 months, defined as proportion of patients who are alive and free of persistent or recurrent NMIBC based on cystoscopy, cytology and/or biopsy. Survival curve for RFS will be generated using the Kaplan-Meier method. Median PFS with 95% CI will be computed. Patients without a recurrence will be censored at their last cystoscopy date.
- g. Cystectomy-free survival (CFS), defined as time from study initiation to cystectomy or death. Survival curve for CFS will be generated using the Kaplan-Meier method. Median PFS with 95% CI will be computed. If CFS cannot be calculated due to not enough patients undergoing cystectomy, it will not be reported.

9. Safety Analyses

a. Adverse Events

- i. Severity of AEs will be graded according to the CTCAE Version 5.0. Adverse events not included in the CTCAE, Version 5.0 must be graded as follows: Mild, Moderate, Severe, Life-threatening, and Fatal according to the following definitions:
 1. Mild: The AE is noticeable to the patient but does not interfere with routine activity.
 2. Moderate: The AE interferes with routine activity but responds to symptomatic therapy or rest.
 3. Severe: The AE significantly limits the patient's ability to perform routine activities despite symptomatic therapy.
 4. Life-threatening: The AE places the patient at risk of death at the time of the event.
 5. Fatal: The AE results in the death of the patient.
- ii. Frequency and severity of adverse events will be tabulated by body system, type and maximum grade. Serious adverse events will be listed.

b. Laboratory Abnormalities

- i. An abnormal laboratory value that is not already associated with an AE is to be recorded as an AE only if any one of the following criteria is met:
 1. an action on the study drug is made as a result of the abnormality
 2. intervention for management of the abnormality is required
 3. at the discretion of the investigator should the abnormality be deemed clinically significant

10. Handling of Missing Data

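### Efficacy results are limited to patients who received at least 5 induction doses and reached a first tumor assessment, which is expected to bias them upward, and the protocol and SAP disagree on the denominator

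*SAP*

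**What the plan says.** **Efficacy set.** SAP 5.c defines it by dosing, "Evaluable patients will be defined as patients who receive at least 5 doses of intravesical BCG and avelumab IV weekly during induction treatment", and by assessment: patients must also "complete the first post-treatment cystoscopy and/or urine cytology for tumor assessment". Protocol 8.2 schedules the first post-treatment cystoscopy and cytology at Month 3. SAP 5.c applies this set to all of SAP Section 8: "Evaluable population will be used for the analysis of EORTC QOQ-C30 (Section 6) and antitumor measures (Section 8". It therefore covers CR (8.b), duration of response (8.c), PFS (8.d), OS (8.e), RFS (8.f) and CFS (8.g). Protocol 8.2.1 has nearly the same definition under an efficacy heading, and the note in Protocol 4.2 refers to 8.2.1 for the meaning of evaluable.

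**Exception and replacement.** Under SAP 5.c, patients with fewer than 5 doses are unevaluable for efficacy and "will be replaced unless the missed doses were due to development of grade 3-4 adverse events related to study treatment". The preceding paragraph has a separate rule, worded in Protocol 8.2.1 as "Patients removed from study for early withdraw or hypersensitivity reactions will be replaced if they have received less than 5 doses of study treatment". Protocol 6.7 says without exception that patients who discontinue treatment prematurely are replaced.

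**Time origins.** For OS, SAP 8.e says "Overall survival (OS) is defined as time in months from first dose of the drug to the date of death". PFS also starts at first dose (8.d). CFS starts at study initiation (8.g). RFS is a proportion at 6 and 12 months with no stated origin (8.f). CR is a proportion at Month 3 or 6 and has no clock (8.b).

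**Protocol analysis set.** Protocol 10.2 says "Only evaluable patients as defined in Section 8.1.1 will be included in the statistical analysis". Section 8.1.1 requires only one dose of BCG and avelumab.

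**Missing data.** SAP Section 10 allows no imputation.

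**The concern.** Whether a patient belongs to the efficacy set is decided by what happens after treatment starts. A patient who dies, withdraws, or stops for intolerance below grade 3 before qualifying is left out, and another patient takes the place. For PFS and OS the clock is already running at first dose, so a death in that window is never counted. For CR there is no clock, and the problem is the denominator: treated patients who never qualify are not recorded as non-responders.

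The losses are unlikely to be random. Protocol 1.5.1 names bladder irritation, fever and flu-like symptoms as reasons why patients may not complete induction, and many such events would fall below grade 3. At stake is whether the anti-tumor results describe everyone who started the combination or only those who tolerated induction and reached an assessment.

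There is also a choice left open. With about 18 patients, two written definitions of the denominator allow it to be settled after the data are seen.

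**Working it through.** **1. The plan's own precision figure.** The only one given is for Month 6 completion (Protocol 10.1, SAP 3.b): n = 18, p = 0.60, two-sided 95% Wilson interval. With z = 1.96, the centre is (p + z²/2n)/(1 + z²/n) and the half-width is z·√(p(1−p)/n + z²/4n²)/(1 + z²/n). This gives 37.6% to 78.9%, so the stated lower bound of 37.6% is reproduced. No assumption is given for CR, PFS, RFS, CFS or OS.

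**2. How many might be excluded.** The documents do not say. Protocol 10.3 and SAP 3.a allow up to 10% dropout: 18/(1 − 0.10) = 20 treated, so 2 excluded. The stated maximum is 27 patients for 18 evaluable. Reading all of the difference as exclusions gives 9. That is an extreme reading, because Protocol 10.1 relates the 27 to evaluation of dose level −1, screen failures and withdrawals.

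**3. Effect on CR.** The count of 8 responders is an assumption. Excluded patients are counted as non-responders.

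| Excluded | CR among all treated | Difference from 8/18 = 44.4% |
|---|---|---|
| 2 | 8/20 = 40.0% | 4.4 points |
| 4 | 8/22 = 36.4% | 8.1 points |
| 6 | 8/24 = 33.3% | 11.1 points |
| 9 (extreme) | 8/27 = 29.6% | 14.8 points |

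If q is the share excluded, the largest relative overstatement is 1/(1 − q), which is 1.11 at 10%. If one of the 2 excluded patients did respond, the all-treated rate is 9/20 = 45.0% and the upward bias disappears.

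**4. Effect on an event-free proportion.** Let S be the proportion in the evaluable set and f the share of excluded patients who fail early, with the rest faring like the others. Then the all-treated value is (1 − q)·S + q·(1 − f)·S. With q = 10% and S = 60% (both assumed), it is 54% for f = 1, 57% for f = 0.5 and 60% for f = 0.

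**5. The uncounted window.** Suppose no event at all could be counted before Month 3 and the hazard is constant. The reported 12-month proportion is then S raised to the power (1 − 3/12). A true 60% would read 68.2%, and a true 95% would read 96.2%. The supposition fits deaths, because a patient who dies before any assessment is out of the set. It does not fit PFS or RFS, because entry requires an assessment to be completed, not to be negative. Recurrence or progression found at Month 3, or at an earlier unscheduled cystoscopy after 5 doses, counts as an event.

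**6. The texts side by side.**

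| Place | Set described |
|---|---|
| Protocol 10.2, citing 8.1.1 | At least one dose |
| Protocol 4.2 note, citing 8.2.1 | 5 doses plus assessment |
| Protocol 8.2.1 | 5 doses plus assessment |
| SAP 5.c | 5 doses plus assessment |

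The replacement rules also collide. A patient stopped before 5 doses by a related grade 3-4 hypersensitivity reaction is replaced under one paragraph of Protocol 8.2.1 and SAP 5.c, is exempt from replacement under the next, and is replaced under Protocol 6.7. The exception does not say whether an exempt patient enters the efficacy set, or still needs the first assessment to do so.

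**The case against.** The strongest reply is that an efficacy-evaluable set is a disclosed and familiar choice in a single-arm phase Ib study with no hypothesis test and a sample size set by feasibility. The endpoints are secondary. Eligibility requires a life expectancy of at least 12 weeks and excludes muscle-invasive and metastatic disease, so early deaths should be few. A 4.4-point shift is also small beside the Wilson interval for 8/18, which runs from 24.6% to 66.3%. All of this stands, and it limits the severity. It does not remove the selection, because a wide interval does not correct a shifted estimate.

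A reader might infer more than the documents support:

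- **That the first 12 weeks are event-free by construction for every endpoint.** They are not, as step 5 shows. Nor do all the clocks start at first dose: that is stated only for PFS and OS.
- **That the bias must favour the combination.** It is expected to, but would be nil if excluded patients fared like the others.
- **That every early toxicity failure is removed.** Doses missed because of related grade 3-4 events fall under the exception.
- **That Protocol 10.2 shows all-treated to be the intended efficacy set.** Section 8.1.1 is headed as a safety definition, so the citation may be a wrong cross-reference. The literal conflict still needs resolving.
- **That the protocol already classes these patients as efficacy failures.** The sentence "Patients who cannot tolerate 5 of 6 weekly treatments as part of induction therapy will be considered treatment failures" follows the definition of the primary endpoint, and the note in Protocol 6.4 concerns BCG induction doses. Neither assigns a status for CR, PFS or OS.

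**Conclusion.** The concern holds in a limited form. SAP 5.c selects the efficacy set on events after first dose, no all-treated efficacy analysis is planned, and the protocol contradicts both itself and the SAP on the denominator. CR and event-free rates are expected to be too high.

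The size cannot be derived. The 4.4-point illustration rests on three assumptions: 8 responders, about 10% exclusion, and no response among those excluded. The timing effect is confined mainly to deaths and exits before assessment, and is small for OS if early deaths are rare: 1.2 points at a true 12-month rate of 95%, under the constant-hazard assumption of step 5.

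This is a should-fix item, because the endpoints are descriptive and secondary. The induction-completion rate in SAP 8.a is outside this point.

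**What to change.** - In SAP 5.c and 8.b-8.g, and in Protocol 8.2.1 and 10.2, make all treated patients (at least one dose, as in Protocol 8.1.1) the main set for CR, PFS, RFS, CFS and OS.
- Count a treated patient with no post-treatment assessment as not in CR, and say that this is a rule of the endpoint, so that it does not conflict with the no-imputation statement in SAP Section 10.
- Time PFS, RFS, CFS and OS from first dose.
- Keep the 5-dose set as a labelled supportive analysis, and report the number excluded with reasons.
- Reconcile the replacement statements in Protocol 6.7, Protocol 8.2.1 and SAP 5.c, including hypersensitivity against the related grade 3-4 exception, so that one rule applies. State whether a patient under the exception enters the supportive set. Which rule governs is for the sponsor to decide.

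The cost is wording only. Protocol 6.9 already follows patients who stop early for response and survival, so no new data collection is planned into this change. The downside is that efficacy rates may look slightly less favourable.
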